9.6 Sample Size Calculation

Based on review of published literature, a hazard ratio of 1.25 is reported (adjusted for the stratification in randomization) for time to clinical improvement in COVID-19 patients receiving anti-viral intervention. The hazard ratio of 1.25 is also assumed to be constant throughout the study as per the assumptions of the Cox proportional hazards regression model with the expected average probability of the event over the course of the study to be 0.9 and 0.8 in test and control group respectively. Inequality testing of the hazard ratio using the Cox proportional hazards regression model with 371 subjects in Favipiravir group and 371 subjects in Placebo group achieves 80% power at the 0.05 significance level for an actual hazard ratio of 1.25 assuming the hazard ratio is 1 under the null hypothesis and that the total number of events achieved is 631. Based on the above assumption and considering the dropout rate to be 5%, overall, 390 patients will be randomized in each treatment group. i.e. 780 patients in total to be randomized in the study. The sample size is estimated using nQuery version 8.5.0.0 using Cox proportional hazard regression. Sample size will be re-estimated based on the analysis of results for the primary endpoint observed during interim analyses.

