10.6 Efficacy Analysis

10.6.1 Primary Efficacy endpoint

Primary Efficacy endpoint will be as follows:

1. Time to resolution of hypoxia

The primary efficacy endpoint is “Time to resolution of hypoxia (Time frame: Up to 28 days)”

This endpoint will be considered to have been met when the patient has attained a score of 4 or lower on the 10-point ordinal scale of clinical status and either of a) or b), (as applicable) and c) is met:

- a) Score is ≤ 4 on consecutive assessments over the next 5 days, if patient continues to remain in hospital (i.e., has not been discharged).

OR

Statistical Analysis Plan
Sponsor: [name], Inc

Study Number: NV-05-983-2020

Version: 2.0 Date: 06JAN2021

- b) Patient was discharged before five consecutive assessments (after reaching a score of 4)

AND

- c) The patient has survived and has not been re-admitted to hospital for COVID-19 management through Day 28.

*Note: Part c) is applicable to patients in both a) and b).
 i.e. Time to resolution of Hypoxia = either "a and c" OR "b and c" is met.*

Time to resolution of hypoxia will be compared between the treatment groups using the Cox proportional hazard model with age, gender, and baseline score on the 10-point ordinal scale of clinical status as covariates. The hazard ratio and its corresponding two-sided 95% confidence interval (CI) and two-sided p -value at 5% level of significance will be obtained from the above Cox proportional hazard model.

As the patients were in the hospital until discharge, missing data in the daily WHO clinical status score were few. To facilitate the definition of the durable response, a very limited and conservative imputation will be implemented to impute a missing clinical status score if adjacent to a valid score on both sides, the imputed score will be the higher (worse) of the two, as discussed in Section 9.5.1.

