 - 2) The next lowest ranks will be given to patients who do not meet the definition of success but are lost to follow-up or are missing endpoint data for Day 28, but survive to Day 28, beginning with the earliest day for which data are lost for the rest of the study.
 - 3) The next lowest ranks will be given to patients who are informative withdrawals – i.e., they withdraw for a reason related to probable treatment failure – but survive to Day 28, beginning with the withdrawals closest to Day 28 (i.e., the latest withdrawals).
 - 4) The next lowest ranks will be given to patients who are followed to Day 28 but do not meet the primary endpoint definition, beginning with patients with the lowest clinical status score on Day 28.
 - 5) The highest (worst) ranks will be given to patients who die, beginning with the deaths closest to Day 28. Thus, the highest rank will be assigned to the first death.

This sensitivity analysis will be done using ITT population.

Listing will be provided for the 10-point ordinal scale of clinical status and oxygen saturation level.

10.6.2 Secondary Analysis:

All secondary analysis will be done using ITT population.

1. Time to discharge from hospital

Time to discharge from hospital = Date of discharge – Date of randomization +1

Statistical Analysis Plan
Sponsor: [name], Inc

Study Number: NV-05-983-2020

Version: 2.0 Date: 06JAN2021

Time to discharge in days will be summarized descriptively. Time to discharge will be compared between the treatment groups using the Cox proportional hazard model. The hazard ratio and its corresponding two-sided 95% confidence interval (CI) and two sided *p*-value at 5% level of significance will be obtained from the above Cox proportional hazard model; Also Median time, quartile, inter quartile range estimate will be presented.

Patients whose does not discharged up to Day 28 will be right censored as of day 28. Patients who discontinue the study for any reason – withdrawal because of an adverse event or worsening of symptoms, switch to rescue therapy, loss to follow-up, etc. – will be right censored at Day 28.

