7. Percentage of patients showing negative conversion of detectable SARS-CoV-2 viral RNA in the RT-PCR assays of respiratory samples on Days 5, 10 and 28 or discharge (if discharge happens earlier than one or more of the above-mentioned timepoints).

Patients showing negative conversion (of detectable SARS-CoV-2 viral RNA) in the RT-PCR assays of respiratory samples on Days 5, 10 and 28 or discharge will be summarized by number and percentage. Two-sided Chi-square test/ Fisher-Exact (Fisher Exact test will be performed when the expected count for any cell is less than 5) test at 5% level of significance will be performed to test the difference of proportion between two treatments.

8. Changes over time in patient's clinical status on the 10-point ordinal scale used in the SOLIDARITY trial by WHO

Statistical Analysis Plan
Sponsor: [name], Inc

Study Number: NV-05-983-2020

Version: 2.0 Date: 06JAN2021

- a. Changes in the 10-point ordinal scale score from baseline until discharge
- b. Proportion of patients in whom clinical status score of 4 ('hospitalized, no oxygen required') or lower has been attained by Days 4, 7, 10, 14, 21 and 28 or discharge (if discharge happens earlier than one or more of the above-mentioned timepoints)
- c. Time (no. of days) from randomization to clinical status score improvement by 1 and by 2 points (from baseline)
- d. Proportion of patients for whom clinical status score improvement by 1 and by 2 points has been attained by Days 4, 7, 10, 14, 21 and 28 or discharge (if discharge happens earlier than one or more of the above-mentioned time points)

Time to Clinical status score improvement by 1 = Date of first time the status trial score improved by 1 following baseline assessment – Date of randomization +1

Time to Clinical status score improvement by 2 = Date of first time the status trial score improved by 2 following baseline assessment – Date of randomization +1

Changes in 10-point ordinal scale score from baseline until discharge will be summarized descriptively by visit and treatment group. The LSM, its 95% CI, and SE will be calculated by treatment group for each measurement point using the Mixed Model Repeated Measures (MMRM) with changes from baseline as an objective variable. Furthermore, differences in LSM between the treatment groups and its 95% CI will be calculated and compared between the treatment groups. Corresponding two-sided *p*-value at 5% level of significance will be presented.

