If the interim analysis results do not suggest early stopping for efficacy or futility, the DMC will consider whether to recommend an increase in sample size, following the method given by Chen, DeMets, & Lan (2004). Conditional power will be calculated under the assumption that the true underlying hazard ratio is the same as the estimate from the current data. If this conditional power is less than 80%, the increase in sample size necessary to make the conditional power 70%, 75%, or 80% will be calculated. If the conditional power with the currently planned sample size is $\geq 50\%$ and the sample size increment required for the desired power is less than approximately 1.5 times the original sample size, increasing sample size by this method will not affect the Type I error rate. In addition, simulations suggest the Type I error in this analysis will not be inflated for conditional power $\geq 20\%$ and $< 50\%$, as long as there is a stopping rule for very low conditional power (Lan & Trost, 1997). If the increase in sample size required to achieve a desired power is not feasible, a smaller increase may be made.

Two key secondary endpoints will also be analyzed in the interim analysis for considering by the DMC in their deliberations. These two endpoints are time to discharge from hospital and time to improvement from baseline of at least 2 points on the 10-point clinical status scale. Cox models and Kaplan-Meier analysis will be employed, as for the primary endpoint. Missing values will not be imputed.

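### Two secondary Cox models name no covariates and three change-from-baseline mixed models name no baseline term, which costs efficiency but not validity

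*SAP*

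**What the plan says.** The primary endpoint is analysed "using the Cox proportional hazard model with age, gender, and baseline score on the 10-point ordinal scale of clinical status as covariates" (SAP 10.6.1).

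In SAP 10.6.2, endpoint 1 has only this: "Time to discharge will be compared between the treatment groups using the Cox proportional hazard model". Endpoint 2 (time until all COVID-19 symptoms are absent or mild) likewise gets a Cox comparison with no covariate named. Other Cox models in the same section do name one: the baseline score of the symptom concerned for endpoint 4, the baseline cycle threshold for endpoint 6, and the baseline 10-point score for endpoint 8c.

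The 10-point score (endpoint 8a) is analysed "using the Mixed Model Repeated Measures (MMRM) with changes from baseline as an objective variable". Chest X-ray RALE (endpoint 10) and NEWS-2 (endpoint 11) are specified in the same way. None of the three names a baseline term.

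For the interim, SAP Appendix I picks two key secondary endpoints, time to discharge and time to a 2-point improvement on the 10-point scale, and says: "Cox models and Kaplan-Meier analysis will be employed, as for the primary endpoint".

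Protocol 11.4.2 leaves secondary methods to the SAP. SAP 10.2 lists age, gender, 10-point score, NEWS, COVID-19 symptoms and RALE among the baseline data.

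**The concern.** The SAP names covariates where it wants them, so a programmer would fit endpoints 1 and 2 with treatment alone. If age, gender and baseline status are prognostic, as their place in the primary model implies, leaving them out of a Cox model gives a hazard ratio closer to 1 and lower power for the same number of events. In a change-from-baseline model, leaving out the baseline value can leave avoidable variance and chance baseline imbalance in the estimate.

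The Appendix I wording adds an ambiguity. It does not settle whether the data monitoring committee and the final report would see the same model for the same endpoint.

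**Working it through.** **1. The plan's own figure.** SAP 9.6 sizes the primary endpoint only. Its power statement is that the design "achieves 80% power at the 0.05 significance level for an actual hazard ratio of 1.25". The event rates are "expected average probability of the event over the course of the study to be 0.9 and 0.8 in test and control group respectively", the number evaluated is "371 subjects in Favipiravir group and 371 subjects in Placebo group", and the event count reads "the total number of events achieved is 631".

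- Events (Schoenfeld, two-sided 0.05, 80% power): 4 × (1.960 + 0.842)² / (ln 1.25)² = 631. Reproduced.
- Patients: mean event probability (0.9 + 0.8)/2 = 0.85; 631/0.85/2 = 371.2 per arm, against 371 stated.
- Power with 631 events: 80.0%.

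No hazard ratio, event rate or power is given for any secondary endpoint, and no prognostic strength for any covariate. What follows is therefore illustrative.

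**2. Cox models with and without covariates.**

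- Borrowed from SAP 9.6: hazard ratio 1.25 (taken as conditional on the covariates), 742 patients allocated 1:1, 80% of controls with an event.
- Assumed: exponential times censored at Day 28, standardised age, 70% male, 30% with baseline score 6, and the prognostic hazard ratios in the table.
- 8,000 simulated trials per row, two-sided 5% test. Simulation error is about 0.5 percentage points, from √(0.8 × 0.2/8000) = 0.0045.

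| Assumed prognostic HRs (per SD of age; male; score 6) | Unadjusted HR | Unadjusted power | Adjusted power |
|---|---|---|---|
| None | 1.25 | 79.5% | 79.3% |
| Weak (0.85; 0.9; 0.7) | 1.24 | 77.0% | 79.5% |
| Moderate (0.75; 0.85; 0.5) | 1.22 | 70.1% | 79.4% |
| Strong (0.6; 0.8; 0.33) | 1.19 | 55.9% | 79.5% |

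The standard error of the log hazard ratio is nearly the same in both models (0.0810 unadjusted and 0.0815 adjusted in the strong row). The power difference comes from the estimate. In the strong row, unadjusted: ln(1.187)/0.0810 = 2.12, and 2.12 − 1.96 = 0.16, which is about 56% power. Adjusted: ln(1.252)/0.0815 = 2.76, and 2.76 − 1.96 = 0.80, about 79%.

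With a true hazard ratio of 1, the rejection rate is 4.7% to 5.3% across both models and all rows.

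**3. Change-from-baseline models at a single visit.** Let k be the baseline SD divided by the post-baseline SD and r the correlation between the two. With post-baseline variance set to 1:

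- without a baseline term, variance = 1 + k² − 2rk;
- with a baseline term, variance = 1 − r².

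The first minus the second is (k − r)², which is never negative, so at one visit the baseline term cannot raise the variance (apart from the trivial cost of one more parameter). Ratios, with over without:

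| k | r = 0.2 | r = 0.3 | r = 0.5 | r = 0.7 |
|---|---|---|---|---|
| 1 | 0.60 | 0.65 | 0.75 | 0.85 |
| 0.5 | 0.91 | 0.96 | 1.00 | 0.93 |
| 0.25 | 1.00 | 1.00 | 0.92 | 0.72 |

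Only the first row (equal SDs) follows (1 + r)/2.

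For the 10-point score, Protocol 4.1.1 requires a baseline score above 4 and Protocol 4.1.2 excludes candidates for mechanical ventilation. Baseline values therefore lie mostly at 5 and 6, while later scores can range from 0 to 10 (Protocol Table 3). A k well below 1 is likely, and the gain may be close to nil. RALE and NEWS-2 may gain more if their baseline and later SDs are similar.

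**4. Interim against final.** If the Appendix I sentence carries over the primary model, time to discharge is adjusted for age, gender and baseline score at the interim and for nothing at the end. The 2-point improvement is adjusted for all three at the interim and for baseline score alone at the end (endpoint 8c). If the sentence refers only to the type of method, there is no mismatch. The text allows both.

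**The case against.** The SAP never calls these models unadjusted; it is silent. The mixed-model text also omits visit, treatment-by-visit and covariance structure, so the missing baseline term may be incomplete description and not a decision. That stands for the mixed models. For endpoints 1 and 2 it carries less weight, because neighbouring endpoints in the same section do name a covariate.

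A reader might go further than the documents allow in four ways.

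- That the unadjusted tests are invalid. They are not: type I error holds.
- That the interim model is definitely adjusted and the final one not. That is one reading of Appendix I.
- That a baseline term would cut the variance to 65-85% in all three mixed models. That range (r from 0.3 to 0.7) needs equal baseline and post-baseline SDs, which is doubtful for the 10-point score.
- That adjustment has no downside. Hazard ratios are non-collapsible, so the adjusted figure estimates a conditional effect and the unadjusted one a marginal effect. Part of the apparent shrinkage is this change of target.

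The Cox power figures also rest on the primary endpoint's hazard ratio and sample size; with weak covariates the loss is only 2.5 points. The guidance appended to the protocol suggests covariate adjustment for the primary analysis, which the SAP already has. All of this limits the size of the point. None of it is a reason to leave the models as written.

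**Conclusion.** The point holds as an efficiency loss. Read as written, the Cox models for time to discharge and time to all symptoms absent or mild are unadjusted, and the three mixed models lack a baseline term.

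Under the borrowed primary sizing and the assumed prognostic strengths, the two Cox models lose roughly 2 to 24 points of power (77.0% against 79.5% at the weak end, 55.9% against 79.5% at the strong end). They would lose essentially nothing by adjusting if the covariates were not prognostic (79.3% against 79.5%). For the mixed models the variance ratio runs from 0.60 to 1.00 over the scenarios checked, and the 10-point score is likely to sit near the top of that range. The direction is firm; the size cannot be fixed from the documents. The Appendix I wording is ambiguous and should be settled in either case.

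**What to change.** Before Stage I database lock and unblinding, and for Appendix I before the unblinded interim is run if it has not been:

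1. SAP 10.6.2, endpoint 1: fit the Cox model with age, gender and baseline 10-point score, as in the primary model.
2. Endpoint 2: use the same three covariates plus a baseline symptom measure, in line with endpoint 4.
3. Endpoints 8a, 10 and 11: add the matching baseline value and its interaction with visit.
4. Label these Cox hazard ratios as covariate-adjusted (conditional).
5. Appendix I: state that time to discharge and the 2-point improvement use the same covariates at the interim and the final analysis, and list them.

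The cost is SAP wording and a few model terms, since all the variables are already collected at baseline. Reusing the primary covariates avoids a data-driven choice. The small downside is that the hazard ratio becomes a conditional estimate; the planned medians and quartiles still describe the unadjusted comparison.

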11.2 General Statistical Considerations

Adverse events and medical history will be classified using standard Medical Dictionary for Regulatory Activities (MedDRA Version 23.0) terminology. Prior and concomitant medications (including medications which are a part of supportive care) will be coded with the World Health Organization Drug Global (WHO-DG, version March 1, 2020) dictionary as applicable.

Unless otherwise specified, the primary efficacy analysis will be done using ITT population. The statistical significance level is 0.05 by one sided or two-sided test, wherever appropriate. Mean/Median estimate (and other general statistics such as Inter quartile range, SD, min, max) and the 95% CI for the estimates of the mean will be provided for the applicable efficacy endpoint. Endpoints will be analysed descriptively and inferentially wherever necessary. Details of the statistical methods will be described in the SAP, which will be finalized before study database lock of Stage I of the study.

Description of statistics:

The primary indicators collected in this study will be described by appropriate statistical methods. To briefly mention, Quantitative indicators will be described by arithmetic mean, standard deviation, median, inter quartile range, maximum, minimum etc.; qualitative indicators will be described by frequency and percentage.

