Patients will be considered as improvement in ALL COVID-19 associated symptoms by Days 4, 7, 10, 14, 21 and 28 will be summarized by number and percentage. Two sided Chi-square test/ Fisher-Exact (Fisher Exact test will be performed when the expected count for any cell is less than 5) test at 5% level of significance will be performed to test the difference of proportion between two treatments.

4. Time to improvement in **EACH** of the symptoms of fever, chills, cough, sore throat, malaise, headache, muscle pain, gastrointestinal symptoms- specifically diarrhoea and vomiting, shortness of breath or dyspnoea by at least 1 grade over baseline.

Note: Severity of symptoms will be evaluated once daily (preferably at or around the same clock time) on each day that the patient is admitted in the hospital. The Investigator/trained study personnel will assess (including by enquiry with the patient, as necessary) and score the severity of each COVID-19 associated symptom on a 5 point Likert-type scale (0= absent, 1= mild, 2=moderate, 3= severe, 4= very severe/critical). The improvement observed must be sustained at evaluations over a period of 24 hours, in order for this secondary efficacy endpoint to be reached.

Time to achieve symptom improvement will be considered to have been met at the earliest timepoint when the particular symptoms score has decreased by at least 1 grade over baseline.

Time to achieve symptom improvement = Date of Change from baseline value for the particular symptom score to become less than or equal to '-1' and sustained at evaluations over a period of 24 hours – Date of randomization +1

Time to achieve symptom improvement will be as follows:

Time to achieve symptom improvement will be summarized for each of the listed COVID-19 associated symptoms descriptively. Time to achieve symptom improvement of the listed COVID-19 associated symptom will be compared between the treatment groups using the Cox proportional hazard model with the baseline symptom score of each symptom as covariate and median time to achieve change from baseline as dependent variable. The hazard ratio and its corresponding two-sided 95% confidence interval (CI) and two sided *p*-value at 5% level of significance will be obtained from the above Cox proportional hazard model; Also Median time, quartile, inter quartile range estimate will be presented.

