Appendix I: Interim Analysis Plan

A single unblinded interim analysis of the primary efficacy endpoint, that is, time to resolution of hypoxia, will be conducted. Resolution of hypoxia is defined as described in Section 10.6.1. This endpoint will be considered to have been met when the patient had attained a score of 4 or lower on the 10-point ordinal scale of clinical status used by the WHO in the SOLIDARITY trial, and either maintained the score of 4 or lower for five consecutive assessments over 5 days or was discharged after reaching the score of 4 or lower. In addition, the patient must also survive and not be readmitted to hospital due to COVID-19 related complications through Day 28 to be considered meeting the endpoint. To be performed when data for time to resolution of hypoxia become available for either the first 390 randomized subjects (50% of the target enrollment) or subjects enrolled by the end of year 2020, whichever is earlier, interim analysis will be conducted for three purposes: 1) Possible early stopping for demonstrated efficacy of the study treatment, 2) Possible early stopping for futility (lack of efficacy), and 3) Sample size reassessment. After reviewing the analysis, the DMC will make a recommendation concerning continuation of the study as planned, termination, or continuation with a larger sample size.

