The interim analysis for efficacy will be performed like the primary efficacy analysis detailed in Section [10.6.1](#) of the Statistical Analysis Plan for the final analysis. Time to resolution of hypoxia will be compared between the treatment groups using the Cox proportional hazard model with age, gender, and baseline score on the 10-point ordinal scale of clinical status as covariates. A Lan-DeMets alpha spending function approach will be adopted in order to maintain the overall Type-I error or alpha at the desired two-sided 0.05 level (Lan & DeMets, 1983). The boundary for possible early stopping for demonstrated efficacy will be determined using a Type I error rate of 0.005 (one-sided); that is, the null hypothesis of zero treatment effect will be rejected if the observed effect is in the direction of treatment benefit and it is significant with one-sided $p < 0.005$. If the trial is not stopped after the interim analysis, the final primary efficacy analysis conducted upon study completion will be based on an adjusted Type I error rate of two-sided 0.04521 (i.e., the result will be considered statistically significant for a Z-statistic ≥ 2.0027).

Assuming the Z-statistic does not reach the boundary for early stopping for demonstrated efficacy, an analysis will be conducted for possible early stopping for futility. A DMC recommendation of early stopping for futility will be based on two factors. The first factor is the conditional power, i.e., the probability of finding a significant beneficial treatment effect with adjusted Type I error rate of two-sided 0.04521 at the end of the study, given the current data and appropriate assumptions about the true treatment effect. The second factor is the estimated effect size from the interim analysis. The DMC may recommend the study be stopped for reasons of futility if either 1) the conditional power is very low (for example, 20% or lower), assuming a hazard ratio equal to the estimated hazard ratio from the current data, or 2) the upper limit of a 95% confidence interval for the difference in median time to resolution of hypoxia is < 1 day. The conditional

Statistical Analysis Plan
Sponsor: [name], Inc

Study Number: NV-05-983-2020

Version: 2.0 Date: 06JAN2021

power will be calculated as in Lachin (2005) and Chen, DeMets, & Lan (2004). Median times to resolution of hypoxia will be estimated by the Kaplan-Meier method.

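### Most secondary endpoints are tested at two-sided 5% with no gate on the primary, no testing order and no statement that the p-values are nominal

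*SAP*

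**What the plan says.** SAP 10.6.2 lists fifteen Stage I secondary items and two Stage II items.

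- The Cox models (items 1, 2, 4, 6 and 8c) yield a hazard ratio, a confidence interval and a two-sided p-value "at 5% level of significance will be obtained from the above Cox proportional hazard model".
- For proportions (items 3, 5, 7, 8b, 8d, 15 and Stage II) the SAP calls for a chi-square or Fisher test. The wording under item 3 is "test at 5% level of significance will be performed to test the difference of proportion between two treatments". Several of these are repeated over a list of days; item 3, for example, is reported "by Days 4, 7, 10, 14, 21 and 28 will be summarized by number and percentage".
- The MMRM analyses (items 8a, 10 and 11) compare the groups at every measurement point, again with a two-sided p-value at 5%.
- Items 13 (log-rank) and 14 (ANOVA) compare the groups but state no level. Items 9 and 12 are summarised without a test.

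Protocol 11.2 supplies only a general default: "The statistical significance level is 0.05 by one sided or two-sided test, wherever appropriate". Protocol 11.4.2 leaves the secondary analyses to the SAP and gives the SAP precedence.

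Appendix I of the SAP states that "Two key secondary endpoints will also be analyzed in the interim analysis": time to discharge, and time to an improvement of at least 2 points on the 10-point scale. They are there to inform the DMC, and the final analysis gives them no special role. For the primary endpoint, the Appendix I efficacy boundary "will be determined using a Type I error rate of 0.005 (one-sided"), and the final test "will be based on an adjusted Type I error rate of two-sided 0.04521". SAP 10.6.1 still prints 5% for the primary.

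**The concern.** A level of significance written against a test is a rule for declaring a result. Here the rule is attached to dozens of tests and depends on nothing else. The plan allows the primary to miss and a secondary to be reported as significant at 5%, chosen from ten symptoms, several repeated days, two improvement thresholds and two daily scores. A real benefit on discharge or clinical status would also be poorly served, because no prespecified rule would separate it from chance findings.

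The silence cannot simply be read as meaning supportive. The SAP does distinguish kinds of analysis elsewhere: items 9 and 12 carry no test, and Appendix I labels the interim mortality and progression analyses exploratory. The tests in 10.6.2 have no such label, and they serve a stated secondary objective on clinical and virological efficacy.

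**Working it through.** **1. The plan's own figure.** Inputs from Appendix I: interim efficacy boundary one-sided 0.005 (z = 2.5758), and interim at "the first 390 randomized subjects (50% of the target enrollment"), taken as an information fraction of 390/780 = 0.5. Solve 1 − P(Z1 < 2.5758, Z2 < c) = 0.025 with correlation √0.5. This gives c = 2.0027, or 0.0452 two-sided, so 0.04521 reproduces. The secondaries at two-sided 0.05 use z = 1.960 against 2.003 for the primary.

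The interim may come earlier, because Appendix I also triggers it at the end of 2020. With the same 0.005 boundary, the final two-sided level would be 0.0441 at a fraction of 0.4 and 0.0430 at 0.3.

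**2. Count of tests in SAP 10.6.2, taken literally.**

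| Item | Comparison | Tests |
|---|---|---|
| 1, 2 | Cox: discharge; all symptoms absent or mild | 2 |
| 3 | Proportion at six listed days | 6 |
| 4 | Cox for each symptom | 10 |
| 5, 6 | Relapse; time to RT-PCR negative | 2 |
| 7 | RT-PCR negative at three time points | 3 |
| 8a | MMRM, 10-point scale, daily Days 2–28 | 27 |
| 8b | Score of 4 or lower at six days | 6 |
| 8c | Cox for 1-point and 2-point improvement | 2 |
| 8d | Two thresholds × six days | 12 |
| 10 | MMRM, chest X-ray, five days | 5 |
| 11 | MMRM, NEWS-2, daily Days 2–28 | 27 |
| 13 | Log-rank, four named comparisons (no level stated) | 4 |
| 14 | ANOVA, five durations (no level stated) | 5 |
| 15 | Deaths, two definitions | 2 |
| Stage II | Relapse; worsening or death | 2 |
| **Total** | | **115** |

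Items 9 and 12 add none.

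**3. How far the count moves.**

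- Tests with an explicit 5% level: 115 − 9 = 106.
- The two daily MMRMs limited to six days each: 115 − 54 + 12 = 73.
- One test per MMRM, for all three: 115 − (27 + 27 + 5) + 3 = 59.
- Smaller choices matter little. Nine symptoms and three log-rank tests give 113; splitting the Stage II worsening item into five gives 119.

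**4. Expected false positives if the drug has no effect on anything.** Expected number = tests × 0.05; in favour of favipiravir = tests × 0.025. Items 13 and 14 are counted at the protocol default of 0.05, taken as two-sided.

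| Reading | Tests | Expected | Favouring favipiravir |
|---|---|---|---|
| Every MMRM time point | 115 | 5.75 | 2.9 |
| Explicit 5% only | 106 | 5.3 | 2.65 |
| Daily MMRMs at six days | 73 | 3.65 | 1.8 |
| One test per MMRM | 59 | 2.95 | 1.5 |

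An expectation adds up whatever the correlation between tests. Fisher's test is conservative, so the figures are slightly high where it applies.

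**5. Effect of a gate.** If secondaries are tested only after the primary succeeds, a false secondary claim under a complete null requires a false primary claim first. Its probability cannot then exceed the primary's overall level: 5% two-sided, or 2.5% in the favourable direction.

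**The case against.** The best defence is that the 5% phrase is reporting boilerplate. The SAP attaches it to the log-rank sensitivity analysis of the primary, which is plainly supportive. There is one primary endpoint, and no secondary has a role in trial success. The protocol speaks only of descriptive and inferential analysis where necessary. On this view a single sentence calling the p-values nominal would be enough. That stands as a description of probable intent. It does not supply the sentence, and the text as written still permits a claim.

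The defence is right to resist three stronger readings.

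- *That 115 tests are each declared at 5%.* 115 is the top of a range. Of these, 54 are daily MMRM contrasts, which the SAP does not clearly say will each be judged significant or not. Nine more state no level.
- *That at least one false positive is almost certain.* That figure needs independent tests. Cumulative proportions on the same patients, and items 8a to 8d on one scale, are strongly correlated. The documents give no basis for an effective number of tests, so no familywise probability should be quoted.
- *That the secondaries face a materially looser standard than the primary.* The gap at the final analysis is 0.05 against 0.04521 and rests on Appendix I alone, since 10.6.1 prints 5% for the primary as well.

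It is also fair to say that Appendix I names its two key endpoints for the DMC only. Promoting and ordering them is a choice that the sponsor would have to make.

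**Conclusion.** The point holds. Neither document has a gate, an order, a multiplicity rule or a nominal label for the secondary tests, and SAP 10.6.2 as written lets secondary significance be claimed after a failed primary. The size is 59 to 115 tests and about 3 to 6 nominally significant results under a complete null, roughly half of them favouring favipiravir. This rests on a literal count of 10.6.2 and on applying 5% to the nine comparisons that state no level.

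A reader might infer that the trial's primary error rate is compromised. It is not: the primary is tested on its own, and its adjusted level reproduces at the planned half-way look. What is exposed is the interpretation of the secondary results. The mismatch between 10.6.1 (5%) and Appendix I (0.04521) is a lesser, separate inconsistency to reconcile.

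**What to change.** Amend SAP 10.6.2 before the Stage I database lock; SAP section 12 has the plan finalised by then.

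1. Test the two endpoints already called key secondary in Appendix I in a fixed, prespecified order, for example time to discharge and then time to an improvement of at least 2 points on the 10-point scale. Test the first only if the primary is met, and the second only if the first is met.
2. Use the primary's threshold for the analysis at which the primary succeeds: one-sided 0.005 if the trial stops for efficacy at the interim, two-sided 0.04521 at the final analysis. A gate tied only to the final threshold would leave no rule after an early stop. If the interim fraction was not one half and the primary's final level is recalculated, the secondaries should follow it.
3. For every other secondary endpoint, including the virological ones, remove the 5% wording. Report the estimate, a 95% confidence interval and a nominal p-value, with no claim of significance.
4. Replace the 5% in SAP 10.6.1 with the Appendix I level.

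The order should be set by people without access to unblinded interim results. The change needs no new data, patients or procedures. Its cost is that no formal claim can rest on the remaining secondary endpoints, so the virological part of the secondary objective would be answered by estimation only.
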